7.2.2 Reporting of Pregnancy and Lactation to the Sponsor and to Merck

Although pregnancy and lactation are not considered adverse events, it is the responsibility of investigators or their designees to report any pregnancy or lactation in a subject (spontaneously reported to them), including the pregnancy of a male subject's female partner that occurs during the trial or within 120 days of completing the trial completing the trial, or 30 days following cessation of treatment if the subject initiates new anticancer therapy, whichever is earlier. All subjects and female partners of male subjects who become pregnant must be followed to the completion/termination of the pregnancy. Pregnancy outcomes of spontaneous abortion, missed abortion, benign hydatidiform mole, blighted ovum, fetal death, intrauterine death, miscarriage and stillbirth must be reported as serious events (Important Medical Events). If the pregnancy continues to term, the outcome (health of infant) must also be reported.

Such events must be reported within 24 hours to the Sponsor and within 2 working days to Merck Global Safety. (Attn: Worldwide Product Safety; [contact])

7.2.3 Immediate Reporting of Adverse Events to the Sponsor and to Merck

7.2.3.1 Serious Adverse Events

A serious adverse event is any adverse event occurring at any dose or during any use of pembrolizumab that:

- Results in death;
- Is life threatening;
- Results in persistent or significant disability/incapacity;
- Results in or prolongs an existing inpatient hospitalization;
- Is a congenital anomaly/birth defect;
- Is a new cancer (that is not a condition of the study);

This document is confidential and the property of the University of Pennsylvania. No part of it may be transmitted, reproduced, published, or used by other persons without prior written authorization from the regulatory sponsor.

- Is associated with an overdose;
- Is an other important medical event

Refer to Table 6 for additional details regarding each of the above criteria.

Any serious adverse event, or follow up to a serious adverse event, including death due to any cause other than progression of the cancer under study that occurs to any subject from the time the consent is signed through 90 days following cessation of treatment (i.e. last dose of pembrolizumab), or the initiation of new anti-cancer therapy, whichever is earlier, whether or not related to pembrolizumab, must be reported within 24 hours of discovery to the Sponsor ([name], [contact] or [name] / page [name]). [name] and the study team will be responsible for reporting SAEs to the University of Pennsylvania IRB, the medical monitor, and the DSMC per reporting of Adverse Events Section 7.3 below. Any serious adverse event must also be reported within 2 working days to Merck Global Safety in the form of a completed CIOMS I/Medwatch. All information shall contain the reporter's name and the Study subject identifier code.

Non-serious Events of Clinical Interest will be forwarded to Merck Global Safety and will be handled in the same manner as SAEs.

Additionally, any serious adverse event, considered by an investigator who is a qualified physician to be related to pembrolizumab that is brought to the attention of the investigator at any time outside of the time period specified in the previous paragraph also must be reported immediately to the Sponsor and to Merck.

7.3 Reporting of Adverse events

HEMATOLOGIC GRADE 3 OR GREATER ADVERSE EVENTS WILL **NOT** BE REPORTED unless they are determined by the Principal Investigator to be unanticipated and clinically significant. **Penn IRB Reporting:**

- (1) Unanticipated problems including suspected adverse reactions and adverse reactions
 - An event is considered a “suspected adverse reaction” when there is *reasonable possibility* that the drug/investigational product caused the adverse event. For these reporting purposes, *reasonable possibility* means there is evidence to suggest a causal relationship between the drug/investigational product and the event.
 - An event is considered *probably or definitely related to the research procedures*.
- (2) In addition to unanticipated problems, the IRB also requires prompt reporting of the following events:
 - Complaint of a participant when the complaint indicates unexpected risks or the complaint cannot be resolved by the research team.

This document is confidential and the property of the University of Pennsylvania. No part of it may be transmitted, reproduced, published, or used by other persons without prior written authorization from the regulatory sponsor.

- Violation or deviation (meaning an accidental or unintentional change to the IRB approved protocol) only when: one or more participants were placed at increased risk of harm, or, the event has the potential to occur again, the event represents serious or continuing noncompliance.
- Breach of confidentiality.
- Incarceration of a participant when the research was not previously approved under Subpart C and the investigator believes it is in the best interest of the subject to remain on the study.

REPORTS MUST BE SUBMITTED ELECTRONICALLY at:
<https://medley.isc-seo.upenn.edu/hsProtocol/jsp/fast.do>

The IRB requires investigators to submit reports within 10 working days (with one exception) of events that meet the definition of an unanticipated problem involving risks to subjects or others. Exception: If the adverse event involved a death and indicates that participants or others are at increased risk of harm, investigators are required to submit a report to the IRB within 3 days.

Penn DSMC Reporting:

- All grade 3 or higher events (unless listed as exclusionary) within ten business days of knowledge
- All unexpected deaths within two business days of knowledge
- All others deaths within 30 days of knowledge. Deaths of subjects off-study for greater than 90 days from the last study treatment/intervention are not reportable

REPORTS MUST BE SUBMITTED ELECTRONICALLY VIA VELOS.

Events will be reported for 30 days following the last study intervention (i.e., last dose of pembrolizumab), or for the protocol defined follow-up if greater than 30 days after the last study intervention.

Penn Medical Monitor Reporting:

- All events reported to the Penn DSMC or non-serious Events of Clinical Interest reported to Merck Global safety will be reported within the same required timeframes as for the Penn DSMC and Merck reporting requirements, respectively. If there are conflicting timeframes, the shorter timeframe will be used.

This document is confidential and the property of the University of Pennsylvania. No part of it may be transmitted, reproduced, published, or used by other persons without prior written authorization from the regulatory sponsor.

- A summary of SAEs and therapy-limiting toxicities will be forwarded to the medical monitor for review after every 3 patients are enrolled and receive at least 4 doses of therapy or every 3 months, whichever occurs first.

Merck: SAE reports and any other relevant safety information are to be forwarded to the Merck Global Safety [contact]

A copy of all 15 Day Reports and Annual Progress Reports is submitted as required by FDA, or other local regulators. Investigators will cross reference this submission according to local regulations to the Merck Investigational Compound Number (IND, CSA, etc.) at the time of submission. Additionally investigators will submit a copy of these reports to Merck & Co., Inc. (Attn: Worldwide Product Safety; [contact]) at the time of submission to FDA.

All subjects with serious adverse events must be followed up for outcome.

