³“All other immune-related AEs” excludes hematologic AEs given that hematologic changes are not considered reportable AEs or treatment-limiting toxicity (Section 7.3, Section 8.1). For grade 3-4 hematologic toxicity at least possibly related to therapy, therapy will be held until toxicity resolves to grade 0-1 or subject’s baseline.

NOTE:

For participants with Grade 3 or 4 immune-related endocrinopathy where withhold of pembrolizumab is required, pembrolizumab may be resumed when AE resolves to \leq Grade 2 and is controlled with hormonal replacement therapy or achieved metabolic control (in case of T1DM).

This document is confidential and the property of the University of Pennsylvania. No part of it may be transmitted, reproduced, published, or used by other persons without prior written authorization from the regulatory sponsor.

Dose modification for cytokine release syndrome:

If patients develop cytokine release syndrome grades 1-3 after pembrolizumab, then pembrolizumab will be held until cytokine release syndrome resolves. Once cytokine release syndrome has fully resolved, the clinical investigator has the option of restarting pembrolizumab at ½ dose (100mg) every 3 weeks. If patients develop grade 4 cytokine release syndrome or require administration of tocilizumab, pembrolizumab will be stopped due to drug toxicity.

Dosing interruptions are permitted in the case of medical / surgical events or logistical reasons not related to study therapy (e.g., elective surgery, unrelated medical events, patient vacation, and/or holidays). Subjects should be placed back on study therapy within 3 weeks of the scheduled interruption, unless otherwise discussed with the Principal Investigator and the Data and Safety Monitoring Board. The reason for interruption should be documented in the patient's study record.

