5.4.2 Cytokine release syndrome and macrophage activation syndrome

Given that pembrolizumab will be administered after patients have received CART-19 therapy, the possibility of re-activating CART-19 cells with subsequent development of cytokine release syndrome exists.

Overview and Clinical Manifestations: Patients treated with pembrolizumab who have previously received CART-19 may experience a cytokine release syndrome (CRS), which has correlated with disease response. Clinical manifestations have included high fevers, fatigue, anorexia, nausea, vomiting, headache, rash, hypotension (occasionally requiring pressor support) tachypnea, hypoxia (occasionally requiring ventilator support), delirium and confusion (in several patients), evidence of disseminated intravascular coagulation as well as macrophage activation syndrome (MAS). In some cases CRS, TLS and hypotension have led to acute kidney injury and several patients have required at least transient dialysis. The CRS has been effectively abrogated with anti-cytokine directed therapy including tocilizumab in most patients. As of July 2014, three patients on another CART-19 trial have died of complications related to refractory CRS and intercurrent infections. It is unclear if treating the CRS adversely impacts the anti-tumor response.

Features consistent with MAS or HLH have been observed in patients treated with CART 19, coincident with clinical manifestations of the CRS. MAS appears to be a reaction to immune activation that occurs from the CRS, and therefore should be considered a manifestation of CRS.

Macrophage activation syndrome (MAS) is similar to Hemophagocytic lymphohistiocytosis (HLH); it is a reaction to immune stimulation by infection, autoimmune diseases or other precipitants, but is distinguished from familial or genetically mediated HLH. There are no definitive diagnostic criteria for MAS, but it is typically diagnosed by meeting HLH criteria.

Some but not all features of MAS are typically observed. The clinical syndrome of MAS is characterized by high grade non-remitting fever, cytopenias affecting at least two of three lineages, and hepatosplenomegaly. It is associated with biochemical abnormalities, such as high circulating levels of serum ferritin, soluble interleukin-2 receptor (sCD25), and triglycerides, together with a decrease of

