Any adverse event that results in hospitalization or prolonged hospitalization should be documented and reported as a serious adverse event unless specifically instructed otherwise in this protocol. Any condition responsible for surgery should be documented as an adverse event if the condition meets the criteria for an adverse event. As was noted above, events related to the cytotoxic chemotherapy will be excluded from adverse event reporting.

Neither the condition, hospitalization, prolonged hospitalization, nor surgery are reported as an adverse event in the following circumstances:

- Hospitalization or prolonged hospitalization for diagnostic or elective surgical procedures for a preexisting condition. Surgery should **not** be reported as an outcome of an adverse event if the purpose of the surgery was elective or diagnostic and the outcome was uneventful.

7.2.1 Definition of an Overdose for This Protocol and Reporting of Overdose to the Sponsor and to Merck

For purposes of this trial, an overdose of pembrolizumab will be defined as any dose of 1,000 mg or greater (≥ 5 times the indicated dose). No specific information is available on the treatment of overdose of pembrolizumab. Appropriate supportive treatment should be provided if clinically indicated. In the event of overdose, the subject should be observed closely for signs of toxicity. Appropriate supportive treatment should be provided if clinically indicated.

This document is confidential and the property of the University of Pennsylvania. No part of it may be transmitted, reproduced, published, or used by other persons without prior written authorization from the regulatory sponsor.

If an adverse event(s) is associated with (“results from”) the overdose of pembrolizumab, the adverse event(s) is reported as a serious adverse event, even if no other seriousness criteria are met.

If a dose of pembrolizumab meeting the protocol definition of overdose is taken without any associated clinical symptoms or abnormal laboratory results, the overdose is reported as a non-serious Event of Clinical Interest (ECI), using the terminology “accidental or intentional overdose without adverse effect.”

All reports of overdose with and without an adverse event must be reported within 24 hours to the Sponsor and within 2 working days hours to Merck Global Safety. (Attn: Worldwide Product Safety; [contact])

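### Section 7.3's exemption for Grade 3 or greater hematologic events has no carve-out for SAEs, so a non-fatal, anticipated hematologic SAE need not reach the DSMC, or the medical monitor promptly

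*Combined protocol and SAP*

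**What the plan says.** Section 7.3 opens with a general exemption, placed ahead of the recipient-by-recipient rules: "HEMATOLOGIC GRADE 3 OR GREATER ADVERSE EVENTS WILL" not be "REPORTED unless they are determined by the Principal Investigator to be unanticipated and clinically significant". The investigator must find both conditions. No exception is made for seriousness or for Grade 5.

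Section 7.2.3.1 requires every SAE to go to the sponsor and the drug supplier. For the other recipients it points onward: SAEs go to the IRB, "the medical monitor, and the DSMC per reporting of Adverse Events Section 7.3 below".

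Within Section 7.3, the DSMC is to receive "All grade 3 or higher events (unless listed as exclusionary) within ten business days of knowledge". Two further DSMC lines cover deaths, with no hematologic exclusion: "All unexpected deaths within two business days of knowledge", and all other deaths within 30 days, except in subjects off study for more than 90 days since their last treatment. The medical monitor's expedited list copies the DSMC list and adds only non-serious events of clinical interest. The monitor also gets a periodic SAE summary.

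Table 3 footnote 3 (Section 5.2.1.2) repeats the exemption with no limit on grade or seriousness: "hematologic changes are not considered reportable AEs or treatment-limiting toxicity".

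**The concern.** Safety is the only primary objective in Section 3.1, and the hazard the trial is built to watch for is re-activation of CAR T cells by pembrolizumab. An exemption for routine laboratory cytopenias is reasonable. This one is drawn by grade, not by seriousness, so it also covers a hematologic event that puts a patient in hospital or is life-threatening.

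The two-part test adds to the problem. An event that is clinically significant but anticipated stays exempt, and the judgement belongs to the Principal Investigator. The toxicity-failure definition in Section 8.1.1 names non-hematologic toxicity and cytokine release syndrome, so the stopping rule does not clearly pick up these events either. What is at stake is whether the DSMC is told of serious hematologic toxicity at all, and whether the medical monitor hears of it in time to act in a 12-patient trial.

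**Working it through.** No arithmetic applies. The check follows two kinds of event through each reporting route.

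**Inputs.** The exemption and the DSMC, IRB and monitor rules (Section 7.3); SAE routing (Section 7.2.3.1); the monitor's remit (Section 10.4); the general reporting statement (Section 7.3.4).

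**Event A:** a Grade 3 or 4 hematologic SAE, non-fatal and anticipated. **Event B:** a fatal hematologic event within 90 days of last treatment.

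| Recipient | Event A | Event B |
|---|---|---|
| Sponsor | Yes, 24 hours (7.2.3.1) | Yes, 24 hours |
| Drug supplier | Yes, 2 working days (7.2.3.1) | Yes, 2 working days |
| DSMC | Not required (7.3 exemption, carried into the Grade 3 or higher line) | Yes, 2 business days if unexpected, otherwise 30 days (7.3 death lines) |
| Medical monitor, expedited | Not required (copies the DSMC list) | Yes (copies the DSMC list) |
| Medical monitor, periodic | Yes, by SAE summary and by review of all AEs at least quarterly (7.3, 10.4) | Yes |
| IRB | Not required under 7.3 | Only as an unanticipated problem |

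**Reasoning for Event A.**

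1. The event is anticipated, so the two-part test fails however clinically significant it is. The exemption applies.
2. Section 7.2.3.1 does not rescue it for the DSMC, because that section hands DSMC reporting to Section 7.3.
3. The DSMC line for Grade 3 or higher events does not rescue it, because that line yields to listed exclusions.
4. The monitor's expedited list does not rescue it, because it contains only what the DSMC receives plus non-serious events of clinical interest. A non-serious event of clinical interest therefore has a prompt route to the monitor that this serious event lacks.
5. The monitor does see it in the SAE summary, sent after every 3 patients with at least 4 doses or every 3 months, whichever is first. The wait is up to three months; a Grade 3 or higher event on the DSMC list would reach the monitor within ten business days.

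**Reasoning for Event B.** The exemption says Grade 3 or greater, which includes Grade 5. The death lines in the same section say all deaths in the window are reportable. Both instructions cannot be followed. The death lines are specific to deaths and carry no exclusion, so the fair reading is a contradiction, not a loophole.

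**Other tensions.** Section 7.3.4 says all adverse events are reported to regulators and IRBs as the law requires, and Section 10.4 gives the monitor all adverse events to review. Neither says how it sits with the exemption.

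**The case against.** The strongest reply is that the plan has several safeguards outside the exemption, and most of it stands. Adverse events are still recorded on the case report forms (Section 7.2), so the exemption affects reporting and not collection. Every SAE reaches the sponsor and the drug supplier by routes that do not pass through Section 7.3. The medical monitor is independent of the trial, reviews all adverse events at least quarterly, and may recommend reporting of events not previously reported, or suspension of the trial. Section 10.4 also provides interim toxicity analyses quarterly or every three patients, and DSMC safety audits. Entry is allowed at a neutrophil count of 1,000, platelets of 50,000 and hemoglobin of 8, so filtering routine cytopenias is sensible.

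These points rule out several stronger readings that a reader might reach:

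- **Fatal hematologic events can go unreported.** The death lines in Section 7.3 require them to reach the DSMC, and so the monitor.
- **Events can be kept from all oversight.** The sponsor, the supplier and the monitor's periodic review all remain.
- **Macrophage activation syndrome escapes.** Section 5.4.2 describes it by, among other features, "cytopenias affecting at least two of three lineages", but treats it as a manifestation of cytokine release syndrome. Section 7.3.3 has its signs reported as that syndrome, which Section 8.1.1 names among toxicity failures. What remains is a cytopenia that someone records as hematologic instead.
- **The IRB loses much.** Its rule in Section 7.3 already turns on unanticipated problems, so an anticipated event would rarely be reportable there anyway.
- **Section 7.2 widens the gap.** Its statement that "events related to the cytotoxic chemotherapy will be excluded from adverse event reporting" looks like leftover text. Section 5.3.2 prohibits chemotherapy during screening and treatment, so it has no evident effect.

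None of these safeguards expressly requires a non-fatal hematologic SAE to be reported to the DSMC, and a quarterly review is not prompt notice.

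**Conclusion.** The point holds in a limited form. Followed to the letter, the plan does not require a non-fatal, anticipated hematologic SAE to be reported to the DSMC, and lets it reach the medical monitor up to three months later. For Grade 5 events Section 7.3 contradicts itself.

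The size is one class of event, missing from one committee and delayed to one monitor. A reader might want an event count, or a comparison with the 30% toxicity target. The documents give no hematologic event rate, and the toxicity-failure definition does not name hematologic events, so neither can be supported.

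The conclusion rests on two assumptions. The first is that the opening exemption is what the DSMC line means by listed exclusions; Section 7.3 offers no other list. The second is that the attached guidance on events of clinical interest, which is not available here, does not add a DSMC route for hematologic events.

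**What to change.** In Section 7.3, limit the exemption to non-serious hematologic laboratory events. State that it does not apply to any event meeting SAE criteria, to deaths, or to cytopenias reported as part of cytokine release or macrophage activation syndrome. Make the reporting wording in Table 3 footnote 3 match.

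The cost is a few sentences in an amendment and a few more expedited reports. Routine cytopenias stay filtered, and no procedures or patients are added.

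Separately, footnote 3 holds treatment for Grade 3-4 hematologic toxicity until recovery with no time limit, while general instruction 2 of Table 3 sets a 12-week limit. The sponsor should reconcile the two; this review does not propose which rule should apply.

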7.3.1.1 Events of Clinical Interest

Selected non-serious and serious adverse events are also known as Events of Clinical Interest (ECI) and must be recorded as such on the Adverse Event case report forms/worksheets and reported within 24 hours of discovery to the Sponsor and within 2 working days to Merck Global Safety. (Attn: Worldwide Product Safety; [contact]).

Events of clinical interest for this trial include:

1. an overdose of pembrolizumab, as defined in Section 7.2.1 - Definition of an Overdose for This Protocol and Reporting of Overdose to the Sponsor, that is not associated with clinical symptoms or abnormal laboratory results.
2. an elevated AST or ALT lab value that is greater than or equal to 3X the upper limit of normal and an elevated total bilirubin lab value that is greater than or equal to 2X the upper limit of normal and, at the same time, an alkaline phosphatase lab value that is less than 2X the upper limit of normal, as determined by way of protocol-specified laboratory testing or unscheduled laboratory testing.*

*Note: These criteria are based upon available regulatory guidance documents. The purpose of the criteria is to specify a threshold of abnormal hepatic tests that may require an additional evaluation for an underlying etiology. The trial site guidance for assessment and follow up of these criteria can be found in the Investigator Trial File Binder (or equivalent).

1. Additional adverse events:

This document is confidential and the property of the University of Pennsylvania. No part of it may be transmitted, reproduced, published, or used by other persons without prior written authorization from the regulatory sponsor.

A separate guidance document has been provided entitled “Event of Clinical Interest Guidance Document” (previously entitled, “Event of Clinical Interest and Immune-Related Adverse Event Guidance Document”). This document can be found in Appendix 4 and provides guidance regarding identification, evaluation and management of ECIs and irAEs.

ECIs (both non-serious and serious adverse events) identified in this guidance document from the date of first dose through 90 days following cessation of treatment, or 30 days after the initiation of a new anticancer therapy, whichever is earlier, need to be reported within 24 hours to the Sponsor and within 2 working days to Merck Global Safety. (Attn: Worldwide Product Safety; [contact]), regardless of attribution to study treatment, consistent with standard SAE reporting guidelines.

Subjects should be assessed for possible ECIs prior to each dose. Lab results should be evaluated and subjects should be asked for signs and symptoms suggestive of an immune-related event. Subjects who develop an ECI thought to be immune-related should have additional testing to rule out other etiologic causes. If lab results or symptoms indicate a possible immune-related ECI, then additional testing should be performed to rule out other etiologic causes. If no other cause is found, then it is assumed to be immune-related.

This document is confidential and the property of the University of Pennsylvania. No part of it may be transmitted, reproduced, published, or used by other persons without prior written authorization from the regulatory sponsor.

